This proposal will provide novel data on tissue-specific response to insulin sensitization with metformin in T1D, cardiac, vascular, exercise and mitochondrial functional response to an insulin sensitizer, potential mechanisms of the response, as well as clarify the role of IR vs. glycemia in these abnormalities. Treating or ultimately preventing IR in all patients with T1D challenges our current approach to T1D care and assumptions about CVD pathophysiology in T1D. We are uniquely poised to address the nature and consequences of IR in diabetic youth. Our ability to perform 3-stage hyperinsulinemic clamps with isotopes in youth with T1D is a rare capability. Our use of non-invasive MRS imaging to assess mitochondrial function with exercise, sophisticated echocardiographic techniques in T1D youth, FPLC lipid subfraction and urine MMP's are all innovative and will generate new data for the field. Our data *will reframe how we think about* the traditional model of IR as synonymous with the metabolic syndrome phenotype and rather will focus on the unique phenotype of IR in T1D.

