and similar numbers of T2D and obese youth, with the P-MRS exercise protocol described. ADP depletion half-time (ADP  $t_{1/2}$ , seconds) following exercise was significantly longer in T1D, despite smaller increases in ADP concentration above pre-exercise concentrations than controls (18±0.4 vs. 29±0.5 mmol/l; p<0.05)[161]. VPCr, the initial rate of phosphocreatine (PCr) resynthesis following exercise, (0.2±0.04 vs. 0.3±0.05) and oxidative phosphorylation (0.09±0.03 vs. 0.16±0.04) were also significantly lower in T1D. In summary, T1D youth performing exercise at equal workloads had less conversion of ATP to ADP, and exhibited delayed post-exercise ATP synthesis. In common with T2D youth[131], T1D youth also had significantly

reduced  $VO_{2peak}$ [119] that independently correlated with IR ( $r=-0.82$ ,  $p<0.0001$ ) in multivariate analysis[119]. HbA1c did not correlate with  $VO_{2peak}$ , suggesting exercise dysfunction is not primarily a function of hyperglycemia. In addition, MRS PCr/Pi post-exercise ratio correlated well with  $VO_{2peak}$  ( $R=0.60$ ,  $P=0.04$ ), indicating muscle MitoD and CV performance are related in T1D. *Our preliminary data suggest muscle MitoD in T1D youth that correlates with IR and decreased  $VO_{2peak}$ , and provides evidence the feasibility of MRS in youth.*

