## 7. Preliminary data showing vascular dysfunction in T1D and T2D youth

Our preliminary results with venous plethysmography show reduced forearm reactive blood flow in T1D and T2D youth[162]. Plethysmography correlated with IR, not A1c, thus non-glycemic factors contribute to vascular function. T1D youth also had significantly reduced  $VO_{2peak}$ [119] that independently correlated with vascular reactivity in multivariate analysis[119, 120]. We previously detected endothelial dysfunction using flow mediated dilation (FMD) in T2D adults[90], one potential cause of the reduced vascular reactivity we report in youth. Vessel stiffness or reduced capillary density may also contribute to abnormal vascular reactivity. Our SEARCH collaborators found peripheral vascular stiffness (BrachD), in T1D youth, especially boys, by Dynapulse[163, 164].

We are also currently assessing baseline endothelial function by FMD, peripheral arterial stiffness with Dynapulse, and central arterial stiffness and atherosclerosis (cIMT) by carotid ultrasound in T1D, T2D, obese and lean nondiabetic youth in our JDRF study. The endo-PAT will measure endothelial function as another non-invasive measurement for comparison. *These studies demonstrate vascular dysfunction related to IR in T1D, our expertise in vascular assessment and the feasibility of these techniques in youth.*

A growing body of literature in the adult population indicated that vascular wall shear stress is significantly higher in vessels with atherosclerotic changes and is an early predictor of atherosclerotic changes. Our hypothesis is that even as young as adolescence, early cardiovascular changes can be detected in youth with diabetes as reflected by abnormal wall shear stress. Aortic wall shear stress can be assessed noninvasively by MRI.

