Secondary Analysis: For all Aims, correlations will also be made between each primary outcome and IR, A1c, T1D duration, and BMI as continuous measures with Pearson correlation coefficients without adjustment for covariates. Multivariate linear regression will determine which outcomes relate independently to IR, A1c, T1D duration, BMI and/or gender after adjusting for covariates. Similar analyses will assess for correlations between changes in IR, A1c and BMI on changes in each primary outcome to the intervention.

Exploratory analyses: Secondary outcomes will be analyzed at baseline and correlations between potential contributors to each outcome will be examined with Pearson or Spearman correlation coefficients, as appropriate. Multivariate linear regression will then determine which potential contributors independently relate to each baseline measure, adjusting for covariates. A mixed effect model will also be used to compare the effects of metformin to placebo on exploratory outcomes.

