The mechanism of IR in T1D is distinct from T2D as the IR phenotype clearly differs. Differentiating each tissue's response to metformin in T1D, and exploring metformin's impact on the CV system will help direct future therapeutic targets, as will clarifying the relative importance of hyperglycemia vs. IR in the cardiac, vascular, exercise and muscle dysfunction in T1D youth. A 2010 meta-analysis concluded that "properly designed randomized controlled clinical trials of metformin" designed to assess "reductions in CVD in T1D should be conducted forthwith"[60]. Our proposal addresses this significant unmet need. Findings supporting directly treating IR in T1D youth may change the clinical approach to T1D care.

T1D shortens lifespan despite modern advances in control of established CV risk factors[207]. Thus, innovative therapeutic approaches are required if we are to address the excess CVD resulting from T1D. Metformin has been attempted previously in T1D youth, but its limited impact on HbA1c tempered enthusiasm. Few studies have examined the non-glycemic benefits of metformin in T1D. Thus, additional benefits of insulin sensitization or clues to causes of IR in T1D may have been overlooked in the literature. The meta-analysis above determined that metformin significantly reduced insulin dose in T1D, but found no trials that included CV outcomes or their surrogates[60]. Therefore, our proposal is highly innovative in assessing metformin's effects on the CV system in T1D. Our proposal also moves beyond the typical paradigm of approaching IR in T1D as strictly a consequence of obesity. Our preliminary data strongly demonstrate two key novel observations: 1. Both T1D and T2D youth have evidence of mitochondrial, vascular, cardiac and exercise dysfunction that correlates with IR. 2. IR is nearly universal in T1D youth but is not predicted by usual metabolic syndrome features, identifying an entirely unique phenotype. Thus, the mechanism of IR is likely also unique in T1D and may respond differently to therapies than it does in T2D. Our data reframe the traditional model of IR as synonymous with a metabolic syndrome phenotype.

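### The stated question of IR versus glycemia has no analysis that compares the two: the secondary regression only sorts predictors into related and unrelated

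*Combined protocol and SAP*

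**What the plan says.** The introduction under Hypotheses and Specific Aims promises to "clarify the role of IR vs. glycemia in these abnormalities", and section IX returns to "clarifying the relative importance of hyperglycemia vs. IR in the cardiac, vascular, exercise and muscle dysfunction in T1D youth". The goal is therefore comparative.

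The Secondary Analysis paragraph of the Data Analysis Plan is what serves it. Each primary outcome is correlated with IR, A1c, diabetes duration and BMI "as continuous measures with Pearson correlation coefficients without adjustment for covariates". Then: "Multivariate linear regression will determine which outcomes relate independently to IR, A1c, T1D duration, BMI and/or gender after adjusting for covariates". The same approach is used for changes: "Similar analyses will assess for correlations between changes in IR, A1c and BMI on changes in each primary outcome to the intervention".

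For these analyses the plan gives no alpha, power, confidence interval, contrast between the IR and A1c coefficients, or rule for reading a null A1c term. The adjusting covariates are not named.

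The preliminary sections show how null HbA1c results have been read. In section 6, HbA1c did not correlate with VO2peak, "suggesting exercise dysfunction is not primarily a function of hyperglycemia". In section 7: "Plethysmography correlated with IR, not A1c, thus non-glycemic factors contribute to vascular" function. Section 10 goes the other way: circumferential strain (CS) correlated with HbA1c (R = 0.35, p = 0.04, 34 adolescents with T1D), and poor control is named as a possible contributor.

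**The concern.** Whether each predictor is related to an outcome is a different question from which of two predictors matters more. One coefficient can be significant and the other not while the two are equal in truth and barely different in the sample. A regression used to determine which outcomes relate to what needs some yes/no criterion, and significance is the only obvious candidate.

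At stake is the interpretation of an announced goal. A finding that an outcome relates to IR but not to HbA1c could be reported as evidence of relative importance when it is only the result of sorting two noisy estimates at a threshold. Nothing in the plan would reveal this.

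**Working it through.** **Inputs**
- N = 80 randomised (Data Analysis Plan, Aim 1a), the upper figure for the baseline model; N = 60 completers (Enrollment), the figure for the change model.
- Two-sided alpha 0.05: assumed. The plan uses 0.05 for Aim 1a and 0.0125 for the other aims, and states none here.
- Five named predictors: IR, A1c, duration, BMI, gender. For the A1c term, k = 4 others (k = 0 for the Pearson test).
- Effect size: none is given for this regression. I use 0.24, the correlation equivalent to a 0.5-SD difference (0.5/√(0.25 + 4) = 0.243), and 0.35 from section 10 of the preliminary data (unadjusted).
- IR–HbA1c correlation 0 to 0.3: assumed.

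**The plan's own figure.** There is none for this analysis. The documented correlation checks: t = 0.35 × √(32/(1 − 0.1225)) = 2.11 on 32 df, p = 0.042, against the stated 0.04.

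**Step 1: chance of missing a real HbA1c effect.** Miss = 1 − Φ(atanh(r) × √(N − 3 − k) − 1.96). For r = 0.24, N = 80, k = 0: 0.2448 × 8.775 − 1.96 = 0.188, so the miss rate is 42.5%.

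| N, k | r = 0.20 | 0.24 | 0.30 | 0.35 |
|---|---|---|---|---|
| 80, 0 | 57% | 42% | 23% | 11% |
| 80, 4 | 59% | 45% | 25% | 12% |
| 60, 0 | 67% | 54% | 35% | 21% |
| 60, 4 | 69% | 57% | 38% | 24% |

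The range over r = 0.20–0.35 is 11–59% at N = 80 and 21–69% at N = 60.

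**Step 2: chance that IR is significant and HbA1c is not when both slopes equal b.** With uncorrelated predictors and all variables standardised, SE ≈ √((1 − 2b²)/(N − 5)). The power of each term is Φ(b/SE − t), with t = 1.993 (N = 80) or 2.005 (N = 60). The pattern has probability power × (1 − power).
- b = 0.24, N = 80: SE = √(0.8848/75) = 0.1086; power = Φ(0.217) = 0.586; 0.586 × 0.414 = 24%.
- b = 0.24, N = 60: SE = √(0.8848/55) = 0.1268; power = Φ(−0.113) = 0.455; 0.455 × 0.545 = 25%.
- b = 0.35, N = 80: SE = √(0.755/75) = 0.1003; power = Φ(1.495) = 0.933; 0.933 × 0.067 = 6%.
- b = 0.35, N = 60: SE = √(0.755/55) = 0.1172; power = Φ(0.982) = 0.837; 0.837 × 0.163 = 14%.

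Simulation of the five-predictor model with IR–HbA1c correlation 0 to 0.3 gives 24–29% at b = 0.24 (N = 60–80), and 7–9% (N = 80) to 14–16% (N = 60) at b = 0.35. By symmetry the reverse pattern is equally frequent.

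**Step 3: the direct contrast.** When the slopes are equal, a test of their difference rejects in about 5%, which is simply its alpha. For true slopes 0.24 and 0, SE of the difference = √2 × √(0.9424/(N − 5)).
- N = 80: 0.1585; power = Φ(0.24/0.1585 − 1.993) = Φ(−0.479) = 32%.
- N = 60: 0.1851; power = Φ(0.24/0.1851 − 2.005) = Φ(−0.708) = 24%.

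Simulation over the same correlation range gives about 24–32% (N = 80) and 19–25% (N = 60).

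**Step 4: could HbA1c be shown to be negligible?** With a true HbA1c slope of 0 and an IR slope of 0.24, the 95% CI half-width is 1.993 × 0.1121 = 0.22 (N = 80) or 2.005 × 0.1309 = 0.26 (N = 60). An interval that wide cannot sit inside a bound such as ±0.2. In simulation it did so in 0% of runs, and in at most 4% with an IR slope of 0.5.

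**The case against.** A reader might infer that the plan contains a significance rule and that a null HbA1c term will be declared proof of IR over glycemia. The documents do not say so. The planned regression already holds IR and A1c together, and the Pearson coefficients will give estimates. Past practice is mixed: section 7 concludes only that non-glycemic factors contribute, section 6 is hedged and concerns a secondary outcome, and section 10 credits HbA1c where it correlated. All of this stands. The significance reading is an inference, though no other criterion is offered.

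A second tempting reading is that an equally strong HbA1c effect is missed about 42% of the time. That needs r = 0.24 at N = 80, and r = 0.24 appears nowhere in the documents. At the documented 0.35 the multivariable miss rate is about 12% (N = 80) to 24% (N = 60). Baseline N might also be larger, since Study Visits speaks of 100 adolescents invited for baseline measurements; at N = 100 and r = 0.24 the Pearson miss rate is 33%. Missing HbA1c is also not the whole error: IR must be significant in the same analysis.

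Third, one might infer that the case for metformin rests on this regression. It does not. Treatment effects come from the randomised comparisons, insulin continues in everyone, and section IX calls intensive glycemic control critical.

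Finally, the contrast has little power at these sample sizes. That is true, and it limits what the remedy can deliver. It does not make sorting by significance a valid comparison.

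**Conclusion.** The concern holds in a limited form. The protocol states a comparative goal, and the Data Analysis Plan has no comparison that could answer it. If readers sort predictors by significance, equal true effects produce the pattern of IR significant and HbA1c not in about 24–29% of analyses per outcome at slopes of 0.24. At slopes of 0.35 the figure is about 7–9% (N = 80) to 14–16% (N = 60).

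These figures assume two-sided 0.05, five predictors and an IR–HbA1c correlation of 0 to 0.3. The 0.24 is assumed; the 0.35 is an unadjusted correlation used as a standardised slope. If 0.35 is taken as a partial correlation instead, Step 1 with k = 4 gives 0.877 × 0.123 = 11% (N = 80) and 0.758 × 0.242 = 18% (N = 60) for independent terms. A stricter alpha would raise the miss rates.

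This is a secondary analysis. It bears on how one announced question is interpreted, not on the validity of the trial, and is worth correcting for that reason.

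**What to change.** Amend the Secondary Analysis paragraph for ADP t½, BrachD and CS. Leave GIR out, because it is itself the IR measure.
- Name the covariates and the alpha.
- From one model per outcome, report standardised IR and HbA1c coefficients with 95% CIs, coded in the same direction (GIR falls as resistance rises, so its sign must be reversed).
- Report the estimate and 95% CI of the difference between the two coefficients. Do the same in the change analysis.
- State that IR matters more than glycemia only if that CI excludes zero; otherwise call the comparison inconclusive.
- State that a non-significant HbA1c term is not evidence of no glycemic effect.

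I would not add an equivalence bound of about ±0.2 for HbA1c, because Step 4 shows it is essentially unattainable at N = 60–80.

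The cost is one linear contrast per outcome and a few sentences, with no new data. The price in conclusions is real: with power of about 19–32% for 0.24 versus 0, many comparisons will be inconclusive. Standardised slopes also depend on the spread of HbA1c in the sample, which the exclusion above 12% truncates, so the contrast is one definition of relative importance and should be described as such.

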#### Analysis plan:

The primary analysis will be a treatment group comparison of mean change in whole body IR (GIR, mg/kg/min, 1o outcome) obtained at the 3 month visit adjusted for baseline IR, tanner stage, sex, and race/ethnicity in an analysis of covariance (ANCOVA) model.

The primary analysis will follow the intent-to-treat principle. The data of all randomized patients will be included in the analysis regardless of whether the assigned treatment was actually received, according to randomization group.

Multiple imputation using Rubin's method 24 will be used to impute the GIR outcomes that are missing. The primary analysis will be repeated including data from participants with no imputation for missing data. The results will be compared with those using imputation to verify that conclusions are not sensitive to the method for handling missing data.

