After an initial screening visit (Table 2 above, Visit 1), 100 T1D adolescents will be asked to come in for initial measurements to obtain baseline measurements. . All participants will undergo the following assessments prior to randomization: a, muscle/aortic MRS assessment (Visit 2, MRS 1) and a cardiovascular and VO2peak assessment (Visit 3, CV 1 ) and hyperinsulinemic euglycemic clamp and Dexa Scan (Visit 4, Clamp 1). After completion of the baseline assessment visits, subjects will then be randomized to 3 months of double-blinded metformin or placebo,. They will have an interim brief visit (Visit 5) to assess blood sugars, insulin dose, compliance and side effects. A phone call will also be done twice in between the baseline and pill count visit and between the pill count and final outcomes visits. At completion of the treatment phase, all participants will undergo repeat outcomes assessments (identical to baseline assessments): a muscle/aortic MRS assessment (Visit 6, MRS 2), a cardiovascular and VO2peak assessment (Visit 7, CV 2 ), and a hyperinsulinemic euglycemic clamp and Dexa Scan (Visit 8, Clamp 2). The treated and untreated Assessments will then be compared to determine the impact of metformin vs. placebo on the outcomes.

**Intervention:** T1D subjects will be randomized by our CTRC pharmacist in a double-blinded fashion at the end of Visit 4 to either active metformin or identical-appearing placebo. Randomization is stratified by: 1) HbA1c above or below 8.5% (mean HbA1c in our preliminary studies) 2) BMI above or below the 85th percentile. The metformin and placebo randomization and dispensing will be done as in our ongoing obesity study (PI [name], COMIRB# 07-0988).

Each participant is provided with a pill dispenser, a calendar to record doses, a study glucose meter and strips, and a log sheet to record glucose levels and insulin dose changes. Participants are asked to check their blood sugar ≥4 times a day, check urine ketones if blood sugar is >than 300mg/dl for more than two readings, and contact the study staff if they have large urine ketones, 2 or more blood sugars <65 mg/dl in any week or any hypoglycemia requiring assistance, any of which will trigger blood sugar adjustment. Subjects will otherwise adjust their insulin as routinely recommended at our center, and are asked not to make changes to the type or

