# **VIII. Data Analysis Plan**

## **A. Data Analysis Plan**

Data analyses and power: For all aims, variables will be checked for the distributional assumption of normality and appropriate transformations applied to normalize the data.

Specific Aim 1a: A placebo-controlled design will be employed using a mixed effect model to determine the effect of treatment and check for the effect of sequence on the effects of metformin to placebo on whole body IR (GIR, mg/kg/min, 1o outcome). Based on the Sarnblad et al article, who had a mean difference of 0.8 and SD of 0.9, with a sample size of 30 per group and an alpha of 0.05, we will have 92% power to detect a difference of 0.8 in the primary outcome of insulin sensitivity. Additional 10 patients will be recruited per/group for a total N = 80 to account for 30% dropout. 100 will be screened to account for screen failures.

Specific Aim 1b: A placebo-controlled design will be employed using a mixed effect model to determine the effect of treatment on the effects of metformin to placebo on ADP t $\frac{1}{2}$  adjusting for baseline mitochondrial function, gender, and Tanner stage. Our preliminary baseline data shows a difference in ADP t $\frac{1}{2}$  between T1D and controls (19.1  $\pm$  0.85 vs. 14.6  $\pm$  0.63, respectively), or an effect size = 5.294. Assuming that T1D patients treated with metformin improve ADP t $\frac{1}{2}$  compared with placebo, we will have > 80% power to detect an effect size as small as 0.645 and a two-sided  $\alpha$  = 0.0125 adjusted for 4 endpoints.

Specific Aim 2a: A placebo-controlled design will be employed using a mixed effect model to determine the effect of treatment on the effects of metformin to placebo on BrachD, adjusting for baseline BrachD, gender, and Tanner stage. Agarwal *et al* demonstrated a mean difference between 3 months of metformin and placebo in young women with PCOS using Aix (-6.1; 95% CI of -8.46-3.74)[93]. If we see a similar effect with common SD = 5.066 calculated from the CI, N = 11 per/group is required for 80% with a two-sided  $\alpha$  = 0.0125 to adjust for 4 endpoints, thus with N = 80 we will have > 99% power for this aim.

Specific Aim 2b: A mixed effect model will be used to compare the effects of metformin to placebo on cardiac dysfunction measured by CS. With N = 80 we will have > 80% power to detect an effect size as small as 0.645 and a two-sided  $\alpha$  = 0.0125 adjusted for 4 endpoints.

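### The primary GIR model omits both randomisation strata, a second GIR model tests a sequence effect that a parallel trial cannot have, and the GIR scale is not settled

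*Combined protocol and SAP*

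**What the plan says.** **Strata.** In Study Visits, under Intervention: "Randomization is stratified by: 1) HbA1c above or below 8.5% (mean HbA1c in our preliminary studies) 2) BMI above or below the" 85th percentile.

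**Primary model.** Under Analysis plan in the Data Analysis Plan section, the primary analysis is a "treatment group comparison of mean change in whole body IR (GIR, mg/kg/min") at 3 months, "adjusted for baseline IR, tanner stage, sex, and race/ethnicity in an analysis of covariance (ANCOVA) model". It follows intention to treat, with multiple imputation of missing GIR. HbA1c and BMI appear only in the correlation and regression analyses.

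**A second model for the same outcome.** Specific Aim 1a in the same section uses a mixed effect model to estimate the treatment effect and "check for the effect of sequence on the effects of metformin to placebo on whole body IR". Study Visits describes a single treatment period: "subjects will then be randomized to 3 months of double-blinded metformin or placebo".

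**Aim 2b.** A mixed effect model "will be used to compare the effects of metformin to placebo on cardiac dysfunction measured by CS", with no covariate named. Aims 1b and 2a adjust for the baseline value, gender and Tanner stage.

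**Scale.** Aim 1a and the Analysis plan both give GIR in mg/kg/min. The third-stage paragraph of Fasting Morning Insulin Clamp normalises GIR to fat-free mass by DEXA. The later clamp calculations express it both per kg of body weight and per kg of fat-free mass.

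**Power.** For a sample of 30 per group, "we will have 92% power to detect a difference of 0.8 in the primary outcome of insulin sensitivity", using an SD of 0.9. Then: "Additional 10 patients will be recruited per/group for a total N = 80 to account for 30% dropout".

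**The concern.** Stratified allocation makes the arms more alike on the strata than simple randomisation would. If a stratum predicts outcome and is left out of the model, the treatment estimate benefits from that balance but its standard error does not: the stratum's variance stays in the error term. The test then rejects less often than its nominal level, and power falls.

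BMI is the stratum more likely to matter. The preliminary data link insulin resistance to BMI even among normal-weight youth and report no association with HbA1c. The inclusion criteria also admit both BMI groups in order to study BMI effects. Baseline IR, already a covariate, will absorb part of any BMI effect.

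The other two items concern how firmly the primary test is defined. Two model descriptions and two GIR scales for one endpoint leave a choice that should not remain open once treatment codes are known. The scale is a real choice: with normal-weight and overweight or obese subjects enrolled, the fat-free fraction of body weight will vary, so the two scales are not a constant multiple of each other.

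**Working it through.** **1. The plan's own figure.** Inputs from Specific Aim 1a: difference 0.8, SD 0.9, 30 per group, alpha 0.05 (taken as two-sided). The noncentrality is (0.8/0.9) × √(30/2) = 3.443. With 58 degrees of freedom the two-sample t-test has 92.3% power (normal approximation 93.1%). The stated 92% reproduces, as an unadjusted comparison of two parallel groups.

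**2. Analytic effect of omitting the strata.** Let R² be the share of the variance left after the four listed covariates that the strata explain. R² is assumed, because the documents give none, and 0.9 is taken as the SD before the strata are removed. With perfect balance on the strata:

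- Error df are about 54 without the strata and 52 with them; critical values are 2.005 and 2.007.
- Type I error without the strata = 2 × P(t₅₄ > 2.005/√(1−R²)).
- Noncentrality for power = 3.443/√(1−R²), compared with 2.005/√(1−R²) (strata out) or 2.007 (strata in).

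| R² | Type I, strata out | Power out | Power in | Loss (points) |
|---|---|---|---|---|
| 0 | 0.0500 | 92.2% | 92.2% | about 0 |
| 0.05 | 0.0445 | 92.7% | 93.4% | 0.66 |
| 0.10 | 0.0392 | 93.3% | 94.5% | 1.28 |
| 0.20 | 0.0291 | 94.3% | 96.5% | 2.23 |

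**3. Simulation with dropout.** At least 60,000 trials per setting (Monte Carlo SE 0.0009 at 0.05).

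- From the documents: 80 randomised, 60 analysed, difference 0.8, SD 0.9, BMI split 40/60 (40% overweight or obese in the registry cited in the preliminary data).
- Assumed: HbA1c split 50/50 (8.5% is the preliminary mean), permuted blocks of 4 within the four strata (no block scheme is stated), 20 lost at random, four random covariates, and all stratum variance carried by BMI.

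| R² | Type I, strata out | Power out | Power in | Loss (points) |
|---|---|---|---|---|
| 0 | 0.0503 | 90.15% | 89.80% | −0.35 (adding them costs 0.35) |
| 0.05 | 0.0468 | 90.54% | 91.17% | 0.63 |
| 0.10 | 0.0432 | 90.92% | 92.48% | 1.56 |
| 0.20 | 0.0357 | 91.71% | 95.00% | 3.29 |

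With the strata in, type I error is 0.0509 throughout (same random draws). Bias is at most 0.0005. Power is about 2 points below the analytic figures because the simulation includes chance imbalance in the four covariates.

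**4. Sensitivity at R² = 0.05, 0.10, 0.20.**

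| Change | Type I, strata out | Loss (points) |
|---|---|---|
| No dropout, 60 analysed | 0.0446, 0.0400, 0.0306 | 0.74, 1.61, 3.07 |
| Blocks of 8 | 0.0462, 0.0431, 0.0361 | 0.72, 1.76, 3.56 |
| Tanner 4 df, race 3 df | 0.0463, 0.0426, 0.0364 | 0.60, 1.91, 4.33 |
| 24 lost (30% of 80), 56 analysed | 0.0458, 0.0433, 0.0365 | 0.70, 1.89, 4.10 |

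A simpler simulation (10,000 runs, 60 completers, no other covariates) splits the variance equally between HbA1c and BMI. At R² 0.10 and 0.20 it gives type I error of 0.037 and 0.032, and power of 93.1 vs 94.4% and 94.0 vs 96.5%. The conclusion does not depend on BMI carrying all the variance.

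**5. Sequence.** A sequence effect needs at least two treatment orders. Here each subject has one assignment and one 3-month period, so no such variable exists.

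**6. Scale.** The 0.8 and 0.9 carry no unit of their own; the outcome in that paragraph is in mg/kg/min. If they are per kg of body weight and fat-free mass is 60% to 85% of weight (assumed), 0.8 becomes 0.8/0.60 = 1.33 down to 0.8/0.85 = 0.94, and 0.9 becomes 1.50 down to 1.06, per kg of fat-free mass. Power is unchanged only if that fraction is the same in every subject. It will not be, so power on the fat-free-mass scale cannot be derived from the documents.

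**The case against.** The strata effect is small and rests on an assumed R². The plan's 92% does not rely on the strata, the BMI link is cross-sectional, and baseline IR is already in the model, so residual R² may be near zero. In that case adding the strata costs a fraction of a point. This stands, and it is why the loss is described as small. It does not favour omission: the possible cost (0.35 to 0.64 points) is smaller than the loss at each non-zero R² examined, apart from near-equality at 5%.

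The simulation analyses completers, whereas the plan imputes missing GIR. This also stands; the figures show direction and order of size, not the exact operating characteristics of the imputed analysis.

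The sequence wording looks like a remnant with no practical effect, and only the ANCOVA text calls itself the primary analysis. That largely settles which model governs, but it leaves two current descriptions for one outcome.

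The clamp calculations report GIR on both scales, and body weight matches the analysis plan. The scale is therefore partly an unreconciled choice; the direct clash is with the third-stage clamp paragraph. The calculations also describe muscle insulin sensitivity by glucose rate of disappearance. However, the aims, the outcome list and both analysis texts name GIR, so that measure is not a rival primary endpoint.

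For Aim 2b, a mixed model of paired measurements can carry baseline in the response. That is possible, but the text does not say so, and Aims 1b and 2a adjust for baseline explicitly.

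**Conclusion.** The concern holds on all three counts. Leaving out the strata is an efficiency matter: no bias, no type I inflation, a mildly conservative test, and a power loss of 0.6 to 3.3 points for residual R² of 5% to 20% (up to 4.3 points in the sensitivity settings). This rests on the assumed R², the assumed block scheme, random dropout and a completer analysis. The sequence check cannot be carried out in this design. The scale conflict is real but no size can be given, because the documents contain no SD on the fat-free-mass scale. The plan should be corrected, but none of this invalidates the trial or its 92% power figure.

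**What to change.** - Keep the ANCOVA under Analysis plan as the single primary model, with its four covariates, and add the HbA1c and BMI strata as used at randomisation. Carry the same terms in the imputation model.
- Delete the mixed model with the sequence check for GIR from Specific Aim 1a.
- Add the strata to the models for ADP t½, BrachD and circumferential strain. Add baseline strain to Aim 2b, with the response stated so that baseline is not entered twice.
- Reconcile the clamp methods with the analysis plan on one primary GIR scale before unblinding, with the other as supportive. State the unit of the 0.8 and 0.9.

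The cost is SAP wording and two degrees of freedom. The strata are known at randomisation, so no new data are needed. Keeping mg/kg/min only requires aligning the clamp text and leaves the power basis as it stands. Moving to fat-free mass would require an SD on that scale and a restated power.
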